## **8.2 Device Supply**

The Triathlon Primary Total Knee System, ShapeMatch® Cutting Guides and eNact Knee Navigation System will be supplied by Stryker Australia Pty Ltd.

## **9.0 SURGICAL PROCEDURES**

### **Group A:**

Each patient will be prepared to undergo a primary total knee replacement using the Triathlon Primary Total Knee System and Stryker eNact Knee Navigation System. A standard skin incision and joint exposure will be performed according to the surgeon's

preference. Navigation trackers will be secured to the femur and tibia and registration of the limb will be undertaken according to the surgical technique.

The appropriate Stryker ShapeMatch® Cutting Guide will be positioned onto the distal femur. A Navigation tracker with Resection Plane Probe attached will be placed into the cutting slot of the cutting guide. The location (position and orientation) of the probe is displayed on the computer screen of the Navigation system. The screen will be diverted from the surgeon's view and a recording will be made of the position once the surgeon has indicated that the cutting guide is positioned appropriately. The cutting guide will then be removed from the femur, and the process repeated until a total of three measurements have been recorded. The same procedure will be performed on the proximal tibia using the appropriate Stryker ShapeMatch® Cutting Guide. This entire process should take no longer than 5 minutes.

Once these measurements have been performed, the surgeon will resume the surgical technique for implantation of the Stryker Triathlon Primary Total Knee System using Stryker eNact Knee Navigation System, as per their own instrument and implant preferences.

Appropriate post-operative care will be provided according to the preference of the treating physician. No further evaluations will be required by study participants.

**Group B:**

Each patient will be prepared to undergo a primary total knee replacement using the Triathlon Primary Total Knee System and Stryker eNact Knee Navigation System. A standard skin incision and joint exposure will be performed according to the surgeon's preference. Navigation trackers will be secured to the femur and tibia and registration of the limb will be undertaken according to the surgical technique.

The appropriate Stryker ShapeMatch® Cutting Guide will be positioned onto the distal femur, and secured in place using fixation pins. A Navigation tracker with Resection Plane Probe attached will be placed into the cutting slot of the cutting guide. The location (position and orientation) of the probe will be displayed on the computer screen of the Navigation system and stored for future reference. The distal femoral

bone resection will be completed and the block removed. Completion of the bone preparation of the distal femur will be undertaken using manual instruments.

The same procedure will be performed on the proximal tibia using the appropriate Stryker ShapeMatch® Cutting Guide.

Trial components will be inserted into the joint and measurements of limb alignment and joint kinematics will be performed using the Navigation system.

Each of these measurements form routine assessments performed during total knee replacement surgery using the Stryker eNact Navigation System.

Once these measurements have been performed, the surgeon will resume the surgical technique for implantation of the Stryker Triathlon Primary Total Knee System using either CR or CS components. If the surgeon identifies intra-operatively that treatment using PS components is deemed more suitable, then this will be carried out. The final choice of components used will be noted on the relevant Case Report Form.

Appropriate post-operative care will be provided according to the preference of the treating physician. Post-operative assessments will be undertaken according to the study protocol.

## **10.0 INFORMED CONSENT**

The Investigator will inform potential study candidates of the purpose of the study, proposed duration of the study, including the study-specific procedures and evaluations. The Investigator will discuss foreseeable risks involved, as well as potential benefits that may result for future participants through the outcomes of this study. Following this verbal discussion with the Investigator, participants will then be given time to read, understand, and, if agreeable, sign the study-specific Participant Consent Form indicating their agreement to participate in the study.

De-identified patient information will be used during the analysis of the results of the clinical study and the confidentiality of the participants will be maintained at all times. Patient records will be stored with the surgeon's normal secure record storage system.

The participants will be informed by the Investigator that they are free to refuse participation in this Investigation, and if they decline or withdraw from the study at any time this will not compromise further medical care.

A signed and dated Participant Consent must be obtained by the Investigator from the patient prior to enrolment into this study. The original signed and dated information sheet and patient consent will be kept by the Investigator. A copy will be provided to the patient, and another copy placed in the patient's hospital medical record.

Should a patient undergo any study procedure without signing a Participant Information and Consent Form, the Investigator must notify the applicable Ethics Committee and study sponsor of the deviation, detailing the circumstances which resulted in the failure to obtain informed consent. The Investigator will then follow Ethics Committee instructions on how to handle patient/situation and obtaining consent.

Patients willing to participate in the extension study will undergo a second consent process with a new patient information sheet detailing the additional study-specific procedures. This process will be carried out in the same manner as the original consent.

## **11.0 EVALUATIONS**

All data will be recorded on the Case Report Forms. The designated signatory (e.g. investigator, delegated authority, participant, etc) will complete and sign forms at the time of each required visit specified by the study protocol.

Only participants in Group B will have detailed information collected pre- and post-operatively as part of their involvement in this study. Participants will have Anterior-

Posterior (AP) and Medio-Lateral (ML) X-rays taken pre-operatively and post-operatively as part of their standard-of-care. In addition, a CT scan according to the Perth CT protocol will be taken post-operatively. Participants will be assessed at 6 weeks, 3 months and 6 months after surgery.

The following data will be captured throughout the study:

**Patient Demographics (Groups A & B):** A record of the patient's date of birth, gender, height, weight, and medical history will be obtained pre-operatively.

**Operative Details (Groups A & B):** A summary of the surgical procedure will be collected during the operation. This will include details of the surgical approach, prosthetic components implanted, operating time and comments. In addition, measurements will be taken intra-operatively using the Stryker eNact Knee Navigation System. This will quantify cutting guide position, limb alignment and limb kinematics during the procedure.

**Medical Imaging (Group B and Extension Study participants only)**

Standard AP and ML X-rays of the affected limb will be obtained pre-operatively and post-operatively. A CT scan according to the Perth CT protocol (Appendix 3; Chauhan et al, 2004) will also be undertaken to obtain detailed three-dimensional descriptions of the position and orientation of the implant components. This position will be compared to the pre-operative plan to assess the efficacy of the customized bone cutting guides to implement the alignment goal.

In the Extension Study, participants will undergo two Long Leg AP weight bearing x-rays to evaluate alignment of the limb; one at 12 months and one at 5 years post surgery.

***Patient outcome measurements (Group B only)***

**The International Knee Society System (IKSS)** separates findings in the operated knee with findings in the patient's function. As such the Knee Score is not artificially affected by co-morbid conditions. The Knee Score consists of points given for pain, range of motion, and stability in both the coronal and sagittal planes, with deductions

for fixed deformity, and extensor lag. The Function Score consists of points given for the ability to walk on level surfaces, and the ability to ascend and descend stairs, with deductions for the use of external supporting devices (Appendix 4; Insall et al; 1990).

**SF-12 v2:** is a multi-purpose, short-form health survey with only 12 questions, derived from the original SF-36. It yields an 8-scale profile of functional health and well-being scores as well as psychometrically-based physical and mental health summary measures and a preference-based health utility index (Appendix 4; Ware, 2000). It is a generic measure, as opposed to one that targets a specific age, disease, or treatment group. Accordingly, the SF-12 has proven useful in surveys of general and specific populations, comparing the relative burden of diseases, and in differentiating the health benefits produced by a wide range of different treatments.

**KOOS:** Self administrating survey form which assesses the patient's opinion about their knee and associated problems. It is designed to assess subjects with relatively high-level of knee joint function and hence can be used to minimize ceiling effects resulting from other less-discriminating knee outcome scores. It consists of 5 subscales: pain; symptoms; function in daily living; function in sport and recreation and knee-related quality of life (Appendix 4; Roos et al; 1998). The original and complete WOMAC Osteoarthritis Index (more typically used for assessment of osteoarthritic knee function) is also contained within KOOS, and can be calculated as a sub-scale.

**VAS:** A Visual Analogue Scale (VAS) is a measurement instrument that tries to measure a characteristic or attitude that is believed to range across a continuum of values and cannot easily be directly measured. For example, the amount of pain that a patient feels ranges across a continuum from none to an extreme amount of pain. From the patient's perspective this spectrum appears continuous - their pain does not take discrete jumps, as a categorization of none, mild, moderate and severe (Wewers et al, 1990).

**FJS-12:** The Forgotten Joint Score is a newly-developed twelve-item, self-reported assessment of how aware recipients of hip and knee joint replacement are of their joint in everyday life (Behrend et al, 2012).

**Medical History Review:** For participants in the extension study, details of any significant medical events from time of surgery to 12 month visit will be recorded to ensure no adverse events have occurred between termination from Group B study and re-enrolment into Extension study.

All information on general medical, operative and device related complications will be documented and tabulated on case report forms (CRF).

All information on complications (date of occurrence, description, severity, related to study device, treatment and resolution) will be recorded at the time of occurrence.

All information on protocol deviations including the type of deviation (informed consent, inclusion/exclusion criteria, treatment, tests not performed and follow-up) will be recorded at the time of occurrence.

## **12.0 STATISTICAL METHODS**

### **12.1 Sample Size Justification**

#### **Group A**

No published data currently exists on the reliability and repeatability of the ability of surgeons to position the patient-specific cutting guides on the femoral and tibial bone surfaces. This is an observational case series with no sample size calculation. The study uses a sample size of convenience, based on the number of study sites and anticipated recruitment rate at each site.

#### **Group B**

Howell et al (2008) reported improvements in post-operative Knee Society Score resulting from the use of ShapeMatch® Cutting Guides for total knee replacement. A comparison of these results with those reported by Matziolis et al (2007) when using computer-assisted surgery for total knee replacement suggests that such differences may be clinically significant. An improvement of 15 points in the Knee Society Score (from 150 to 165 points, out of a maximum of 200) with a standard deviation of 35 can be assumed as representing a clinical significant improvement. Using these figures,

with 80% power, power analysis indicates that 87 patients per group are required. This does assume comparison of two independent groups with the t-test. Allowing for patient drop out, a minimum of 100 cases is recommended.

All 100 cases will be invited to participate in the Extension Study.

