### **3.0 OBJECTIVES**

The primary endpoints of this study are:

1. Repeatability of cutting guide position on the distal femur and proximal tibia assessed by repeated measures using computer navigation system for total knee replacement, assessed intra-operatively (Group A).
2. Radiographic implant location, consisting of multi-parameter assessment of the relative position and orientation of the femoral and tibial components and overall limb alignment, assessed by the Perth CT protocol 3 months after surgery (Group B).

The secondary endpoint of this study is:

3. Knee function, quality of life and pain assessed 6 months after surgery (Group B).

The study objectives are:

1. Repeatability of the cutting guide position will be no worse than that obtained for manual instruments used for total knee replacement (Group A).

2. Participants will have higher knee function scores and increased quality of life as compared to pre-operative state and equal or better as compared to other surgical techniques using historical controls (Group B)

The objectives of the Extension Study are:

1. The primary objective is to determine the clinical and radiographic outcomes at 12 months, 2 years and 5 years post surgery, in patients receiving a Triathlon Custom Fit Knee featuring Stryker ShapeMatch.
2. The secondary objective is to determine the revision rate (yearly cumulative percent revision), device-related adverse events and reoperation rates.

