## RESEARCH OBJECTIVES

The use of patient-specific cutting guides for total knee joint replacement is being developed and introduced to clinical practice by a number of orthopaedic device companies. Each system differs in the way in which the cutting guides are designed, the material which they are made from, the alignment philosophy and the radiological information on which they are based (e.g. X-ray, CT, MRI).

The overall goal of this study is to assess the impact of a new surgical technique developed by Stryker on the functional outcome of participants undergoing primary total knee joint replacement.

The repeatability in placing the cutting guides relies on the reference points used in the design of the block, and the ability of the surgeon to position it on the diseased joint surfaces of the knee without the availability of traditional alignment jigs (femoral intra-medullary rod, tibial extra- or intra-medullary alignment guide). Hence, the first objective of this study is to quantify the reproducibility of this new technique by assessing cutting guide position using a repeated-measures methodology. The results will be described as a standard error of measurement.

Early reports indicate that improved post-operative functional outcomes may result from the use of this new technology when used in combination with particular designs of total knee joint prosthetic components (Howell et al, 2008; Spencer et al, 2009). The second objective is to assess and quantify such changes in the short-term (6

months) post-operative period. Potential benefits may be seen in the general quality of life experienced by participants, reduced pain levels, and specific improvements in activities of daily living affected by knee function. Other parameters related to the procedure, such as operating time, blood loss and length of stay in hospital will also be assessed to determine if perceived benefits with the use of this new surgical technique can be realised in routine clinical practice. Comparison of the study findings will be made to published literature on the clinical outcomes of total knee replacement (e.g. Kolisek et al, 2007; Matziolis et al, 2007; Harwin et al, 2008).

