**7.0 STUDY DESIGN**

**Group A:** This is a repeatability study of ShapeMatch® patient-specific cutting guides designed for participants undergoing total knee arthroplasty with the Triathlon® Total

Knee System (Stryker Orthopaedics, Mahwah NJ, USA) and Stryker eNact Knee Navigation System (Stryker Navigation, Kalamazoo MI, USA). Participants will undergo pre-operative assessment using MRI of the affected limb according to the scan protocol (see Appendix 2 for example). At the time of surgery, a repeated-measures methodology will be implemented in which the position of the femoral and tibial cutting guides will be measured using the Navigation system. The same surgeon will position each cutting guide a total of 3 times for each patient. Multiple participants will be assessed by each surgeon. No bone resections will take place using the patient-specific cutting guides. After the study-specific measurements have been taken, the total knee procedure will resume using the Navigation system and associated instruments being used to prepare the distal femur and tibia prior to implantation of the Triathlon® total knee components. No post-operative evaluations will be undertaken as part of this sub-study. However, participants will have routine visits, as per the investigators' standard-of-care for such participants.

Approximately 30 participants (5 per investigator) up to a maximum of 60 participants will contribute to this sub-study.

**Group B:** This is a consecutive sample survey of participants undergoing total knee arthroplasty with the Triathlon® Total Knee System (Stryker Orthopaedics, Mahwah, NJ USA) utilizing ShapeMatch® patient-specific cutting guides to prepare the bony resections on the distal femur and proximal tibia. Health status and functional outcome measures will be recorded to quantify functional status of subjects before surgery and at each follow-up interval.

Participants suitable for primary total knee arthroplasty and indicated for computer-assisted surgery will be booked for surgery. Recruitment will be subject to gaining suitable informed consent from the patient.

Participants will undergo pre-operative assessment using MRI of the affected limb according to the scan protocol (Appendix 2).

Appropriate total knee replacement components from the Stryker Triathlon® Total Knee System will be used.

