## **12.2 Data Capture and Analysis**

All data will be recorded on 2-part NCR paper Case Report Forms (CRFs). The surgeon will complete and sign forms at the time of completion. Original CRFs will be collected by Stryker for data entry. Copies will remain at the investigator site. Archiving will be undertaken in accordance with ICH/GCP guidelines (Appendix 6).

Any unclear or ambiguous data will be queried and all cleaned data will be entered into a database for tracing purposes.

The primary outcome data gathered from Group A will be assessed using a repeated-measures analysis (Hopkins, 2009) to determine the mean and standard error of measurement between successive pairs of trials. Multiple surgeons gathering repeated measures on individual patients will be pooled to take into account varying knee anatomies and intra-observer variation.

The data from Group B and the Extension Study will be summarised and descriptive statistics will be utilised for analysis of the primary and secondary outcomes. The mean, median, standard deviation, minimum and maximum will be presented for quantitative variables. Statistical tests will be employed as deemed appropriate by a biostatistician. A significance level of 0.05 will be used for comparative tests.

Adverse events will be tabulated separately and reviewed for any commonalities.

Revision surgery data from the Extension Study will be compared to the revision rates reported in the National Joint Registry Report at 12 months, 2 years and 5 years. A cost benefit analysis will be undertaken with the use of data from the Australian Government Hospital Casemix Protocol Annual Report.

A formal interim analysis will take place following completion of each Group A and Group B sub-studies. Additionally, formal interim analyses will take place following all

participants' completion of the 12 month visit, again following completion of all participants' 2 year visit and final analysis will take place following completion of all participants' 5 year follow-up visits.

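### Group B's 80% power assumes two independent groups of 87, but the trial recruits one cohort and fixes no historical series, so the 80% is not established for this design.

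*Combined protocol and SAP*

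**What the plan says.** Section 12.1 (Group B) takes an improvement from 150 to 165 points on the 200-point Knee Society Score, SD 35, as clinically significant. It then states: "power analysis indicates that 87 patients per group are required. This does assume comparison of two independent groups with the t-test". An unstated drop-out allowance raises 87 to 100. Two published series, one custom-fit and one computer-assisted, motivate the 15 points.

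The rest of the protocol describes a different structure:

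- Sections 1.0 and 4.0: a non-randomised study in which Group B is a single cohort of 100 cases.
- Section 7.0, on Group A: "No post-operative evaluations will be undertaken as part of this sub-study".
- Section 3.0 sets two comparisons for Group B. The first is with baseline: "Participants will have higher knee function scores and increased quality of life as compared to pre-operative state". The second is with outside data: "equal or better as compared to other surgical techniques using historical controls (Group B)".
- Section 3.0 makes the scores the secondary endpoint: "Knee function, quality of life and pain assessed 6 months after surgery (Group B)". The Group B primary endpoint is implant position on CT.
- Research Objectives: "Comparison of the study findings will be made to published literature on the clinical outcomes of total knee replacement". The series that follow, including the computer-assisted one, are given only as examples.
- Section 12.2: "descriptive statistics will be utilised for analysis of the primary and secondary outcomes", and then "Statistical tests will be employed as deemed appropriate by a biostatistician. A significance level of 0.05 will be used for comparative tests".

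**The concern.** A two-sample power figure belongs to a comparison of two groups of known size. Here one group is recruited. The other would have to come from published literature, and no series is fixed with its n, mean and SD. Section 12.1 discloses the two-group assumption, but no section reconciles it with the single-cohort design.

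This matters because the 80% is the only quantitative basis for Group B's 100 cases. Section 3.0 keeps a historical-control objective and section 12.2 sets a 0.05 level for comparative tests, so such a test remains possible, and a reader would take 80% as its power. If the series is chosen after the results are known, both the power and the conclusion depend on that choice.

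Two related gaps follow. A calculation for detecting a difference does not support a claim of equality without a margin, and none is given. Section 12.1 also does not say that it concerns a secondary endpoint, and it does not address the baseline comparison, which a single cohort can support.

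**Working it through.** **Inputs.** From section 12.1: difference 15, SD 35 (one value, applied to both groups), power 80%, 87 per group, t-test. From section 12.2: alpha 0.05. Sidedness is not stated. The 100 recruited against 87 required implies a 13% allowance (1 − 87/100).

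**1. Reproduce the plan's figure.** For group sizes n and m, the noncentrality is 15 / (35 × √(1/n + 1/m)) on n + m − 2 degrees of freedom.

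- 87 v 87: SE = 35 × √(2/87) = 5.31; noncentrality 15/5.31 = 2.83; two-sided 0.05 power 80.3%.
- 86 v 86: 79.8%. So 87 is the smallest n per group.
- One-sided 0.05 would need only 69 per group (80.5%). The plan's figure is therefore inferred to be two-sided.

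The arithmetic is correct for its model. That model needs 2 × 87 = 174 evaluable patients in two groups, and the trial supplies one of them.

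**2. Power against a historical series of size m.** The documents give no m, so the sizes below are assumptions. SD 35 is assumed in both groups, with no systematic difference between the series.

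| Historical m | 87 evaluable | 100 evaluable |
|---|---|---|
| 30 | 52% | 53% |
| 50 | 67% | 69% |
| 87 | 80% | 83% |
| 200 | 91% | 94% |

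The smallest m that reaches 80% is 86 with 87 evaluable, or 77 with all 100 evaluable (76 gives 79.98%).

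**3. What one cohort delivers without a comparator.** The 95% CI half-width for the mean is t × 35/√n.

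- n = 87: 1.988 × 35/√87 = 7.5 points.
- n = 100: 1.984 × 35/√100 = 6.9 points.

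**4. Paired change from baseline, 87 pairs.** SD of change = 35 × √(2(1 − ρ)), assuming SD 35 at both visits. The correlation ρ is assumed. So is the use of 15 points as a within-patient change, because section 12.1 introduces that figure by comparing two techniques.

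| ρ | SD of change | Half-width | Power for 15 points |
|---|---|---|---|
| 0 | 49.5 | 10.5 | 80% |
| 0.3 | 41.4 | 8.8 | 92% |
| 0.5 | 35.0 | 7.5 | 98% |
| 0.7 | 27.1 | 5.8 | 99.9% |

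**5. A tempting shortcut.** Treating a published mean as a known constant (a one-sample t-test) would appear to give 97.7% power with 87 patients. It ignores the sampling error of the published mean. With equal SDs, the true two-sided type I error is 2 × P(t₈₆ > 1.988/√(1 + 87/m)): 23% for m = 50, 16% for m = 87 and 10% for m = 200, against a nominal 5%.

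**6. Bias lies outside any of these figures.** As an illustration at 87 v 87, a 5-point systematic difference between series that offsets the effect leaves 10 points and cuts power to about 47%. A spurious 5-point difference with no true effect is declared significant about 16% of the time.

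**The case against.** The strongest reply has four parts.

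- **The assumption is disclosed, and its error has no known direction.** Section 12.1 states the two-group basis openly, and true power could be above or below 80%. Nothing shows that 100 is too few. This stands, and it is why the claim is only that 80% is not established. Disclosure still does not supply the second group.
- **The study presents itself as a case series with a mainly descriptive analysis, and defers stronger evidence to later randomised trials.** This also stands and limits the harm. But if the analysis is descriptive, precision is the natural justification for n, not power, and sections 3.0 and 12.2 still leave a historical test open.
- **The computer-assisted series could be read as the planning comparator.** That is a fair reading of how the 15 points arose. However, section 12.1 attributes neither the 150 nor the SD to it and does not name it for analysis, and Research Objectives lists it only as an example. The percentages in step 2 are illustrations over assumed sizes, not measurements of this trial.
- **Sizing on a secondary endpoint is legitimate, and the documents do not propose a one-sample test.** Both are true. The first only needs saying in section 12.1. The second is a caution for whoever chooses the test that section 12.2 leaves open.

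**Conclusion.** The concern holds and should be fixed; confidence is high. The 87 per group is computed correctly for two independent groups, two-sided 0.05, but this trial has one group and no fixed comparator.

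The size of the gap depends on a series that the documents do not identify: about 52% to 91% power with 87 evaluable over assumed sizes of 30 to 200, reaching 80% only from 86 historical patients upward. These figures rest on SD 35 in both groups and no bias between series. The baseline objective is not undermined, because a single cohort supports it without any control series. The mainly descriptive plan and the secondary status of the score keep this below a critical fault.

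**What to change.** **Section 12.1.** Replace the two-group power statement with one that fits a single cohort.

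- *Default, consistent with section 12.2:* state precision, a 95% CI half-width of about 7.5 points with 87 evaluable patients at SD 35.
- *Alternative:* name one historical series before the Group B results are seen, and give two-sample power from its actual n, mean and SD. Do not use a one-sample test that treats the published mean as known.

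In either case, say that the calculation concerns a secondary endpoint and that the pre- to post-operative comparison is a paired within-patient analysis needing no control series.

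**Section 12.2.** Report the difference from the historical series with its 95% CI. State that a non-significant result will not be read as equality, and that the comparison is descriptive unless a margin was set before the Group B results were seen. The documents do not show whether those results are already known. If they are, only the descriptive form remains.

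**Cost.** An amendment with written ethics approval (section 18.0): one paragraph in 12.1, one or two sentences in 12.2, and no extra patients. The drawback is a possibly less favourable figure, for example 52% or 67% power if the named series has 30 or 50 patients. The precision form gives up the power claim altogether.
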